5.2. Criteria for eliminating data from Analysis Sets

Elimination codes are used to identify subjects to be eliminated from analysis. Detail is provide below for each sets.

5.2.1. Elimination from TVC

Code 1030 (Study vaccine dose not administered at all but subject number allocated) and code 900 (invalid informed consent or fraud data) will be used for identifying subjects eliminated from TVC.

5.2.2. Elimination from ATP cohort for analysis of immunogenicity

A subject will be excluded from the ATP cohort for analysis of immunogenicity under the following conditions:

| Code Eli Type =MA | Condition under which the code is used |
|----------------------|---|
| 900 | Invalid informed consent or fraud data |
| 1030 | Study vaccine dose not administered at all but subject number allocated |
| 1040 | Administration of concomitant vaccine(s) forbidden in the protocol up to blood sample at visit 7 |
| 1050 | Randomisation failure (subject not randomized in the correct group) |
| 1070 | Study vaccine dose not administered according to protocol: - Site or route of study vaccine administration wrong or unknown - Administration not according to protocol for reason specified by the investigator other than site and route - Wrong replacement or study vaccine administered (not compatible with the vaccine regimen associated to the treatment number) - Only part of the multiple planned administrations at one visit has been administered |
| 1080 | Vaccine has been administered (effective treatment number) despite a temperature deviation qualified by Status QA GMP NON Use |
| 1090 | Vaccine has been administered (effective treatment number) out of the expiration date at the time of administration |
| 2010 | Protocol violation linked to the inclusion/exclusion criteria |
| 2040 | Administration of any medication forbidden by the protocol up to blood sample at visit 7 |
| 2050 | Underlying medical condition forbidden by the protocol up to blood sample at visit 7 |
| 2060 | Concomitant infection related to any component of the DPT-IPV vaccine which may influence the immune response up to blood sample at visit 7 |
| 2070 | Concomitant infection not related to any component of the DPT-IPV vaccine other than RV GE which may influence the immune response up to blood sample at visit 7. Note that RV GE will not be considered as concomitant infection unrelated to any component of the DPT-IPV vaccine. |
| 2080 | Non compliance with vaccination schedule for HRV and/or DPT-IPV vaccination – see Table 4 |
| 2090 | Non compliance with blood sample schedule at Visit 7 – see Table 4 |

| Code Eli Type =MA | Condition under which the code is used |
|----------------------|---|
| 2100 | Essential serological data missing: serological data missing for all antigens in the DPT-IPV vaccine at Visit 7 |
| 2120 | Obvious incoherence, abnormal serology evolution or error in data (Eg; incoherence between CRF and results, wrong sample labelling) |

Table 4 Intervals between study visits for code 2080 and 2090

| Study Group | Interval | Optimal length of interval ¹ | Allowed interval ² |
|-------------------------|-------------------|---|-------------------------------|
| Co-administration group | Visit 1→Visit 2* | 30 days | 28 days - 42 days |
| | Visit 2→Visit 4 | 30 days | 28 days – 42 days |
| | Visit 4→Visit 6 | 56 days | 28 days - 56 days |
| | Visit 6→Visit 7 | 30 days | 21 days - 48 days |
| Staggered group | Visit 1→Visit 2* | 30 days | 28 days - 42 days |
| | Visit 2→Visit 3 | 15 days | 7 days - 21 days |
| | Visit 3→Visit 5** | 30 days | 28 days - 42 days |
| | Visit 5→Visit 6 | 45 days | 28 days – 56 days |
| | Visit 6→Visit 7 | 30 days | 21 days - 48 days |

¹. Whenever possible the investigator should arrange study visits within this interval.

². Subjects will not be eligible for inclusion in the According To Protocol (ATP) cohort for analysis of immunogenicity if they make the study visit outside this interval.

* Visit 2 should take place when the subject is 3 months of age or older.

**The period between Visit 2 and Visit 5 should be within 8 weeks.

There should be a time-period of at least 7 days between the administration of an inactivated vaccine and any other vaccine, and 28 days between the administration of a live virus vaccine and any other vaccine, in Japan. Please refer to the package inserts of *Rotarix* and *Squarekids* for more details.

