2. STUDY DESIGN

N = Number of subjects planned to be enrolled; n = Number of subjects in each group; BS = Blood Sampling. Visit 3 and Visit 5 are applicable only for subjects in the Staggered group. Visit 4 is applicable only for subjects in the Co-administration group.

- Experimental design: Phase IV, open-label, randomised, controlled, multi-centric, single-country study with two parallel groups.
- Primary Completion Date: Visit 7 (Month 5)
- End of Study: Last testing results released of samples collected at Visit 7
- Study groups: The study groups and epoch foreseen in the study are provided in Table 1.

Table 1 **Study groups and epochs foreseen in the study**

| Study Groups | Number of subjects | Age (Min/ - Max) | Epoch |
|-------------------------|--------------------|--------------------|-----------|
| | | | Epoch 001 |
| Co-administration group | 146 | 6 weeks - 12 weeks | x |
| Staggered group | 146 | 6 weeks - 12 weeks | x |

- The study groups and treatment foreseen in the study are provided in Table 2.

Table 2 Study groups and treatment foreseen in the study

| Treatment name | Vaccine name | Study Groups | |
|----------------|--------------|-------------------------|-----------------|
| | | Co-administration group | Staggered group |
| Rotarix | HRV | x | x |
| Squarekids | Squarekids | x | x |

- Control: active control (Staggered group).
- Vaccination schedules: The vaccination schedules are as follows:
 - Subjects in the Co-administration group will be administered the DPT-IPV vaccine according to a 3, 4, 6 month schedule and the liquid HRV vaccine according to a 2, 3 month schedule.
 - Subjects in the Staggered group will be administered the DPT-IPV vaccine according to a 3, 4.5, 6 month schedule and the liquid HRV vaccine according to a 2, 3.5 month schedule.
- Treatment allocation: Randomised 1:1 using GSK Biologicals' central randomisation system on Internet (SBIR). The randomisation algorithm will use a minimisation procedure accounting for centre and stratified for a HRV immunogenicity sub-cohort.
- Blinding: Open-label.
- Sampling schedule: Details of the samples to be collected are as follows:
 - A blood sample of approximately 2 mL will be collected from a sub-cohort of subjects, 1 month after the administration of the second dose of the liquid HRV vaccine.
 - A blood sample of approximately 5 mL will be collected at Visit 7, 1 month after administration of the last dose of DPT-IPV vaccine from all the subjects.

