6.3. Immunogenicity

6.3.1. Analysis of immunogenicity planned in the protocol

The ATP cohort for immunogenicity will be used for the primary analysis of immunogenicity. An analysis of immunogenicity based on the TVC will be performed

only if more than 5% of the vaccinated subjects with immunogenicity results available were excluded from the ATP cohort for immunogenicity. In such a case, the TVC analyses will evaluate whether exclusion from the ATP cohort has biased the results.

Within group assessment

For each treatment group and each antigen:

- Percentage of subjects with antibody concentrations/ titres greater than or equal to the pre-specified cut-off will be calculated with exact 95% CI (Refer Table 9 of the protocol). Anti-PT and anti-FHA antibody concentrations ≥ 10 IU/mL will also be calculated with exact 95% CI.
- GMC/GMTs, as applicable with 95% CIs will be computed.
- The distribution of antibody concentrations/ titres, as applicable, will be presented using reverse cumulative curves (RCCs).

Between group assessment

For each antigen in the DPT-IPV vaccine:

- The two-sided asymptotic standardised 95% CIs for the difference between groups (Co-administration group minus Staggered group) in terms of percentage of subjects with antibody concentrations/ titres greater than or equal to the pre-specified cut-off will be computed. Anti-PT and anti-FHA antibody concentrations ≥ 10 IU/mL will also be calculated with exact 95% CI.

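### The Co-administration target for DPT-IPV dose 2 to dose 3 (56 days) is also its ATP exclusion limit, while the Staggered arm has 11 days of room after its target

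*SAP*

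**What the plan says.** Table 4 in SAP Section 5.2.2 lists, for each visit interval, an optimal length and an allowed range. For DPT-IPV dose 2 to dose 3 the two rows are:

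- Co-administration: "Visit 4→Visit 6 | 56 days | 28 days - 56 days"
- Staggered: "Visit 5→Visit 6 | 45 days | 28 days – 56 days"

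Footnote 1, on the optimal length, reads: "Whenever possible the investigator should arrange study visits within this interval". Footnote 2, on the allowed range, makes infants ineligible for the ATP cohort "for analysis of immunogenicity if they make the study visit outside this interval". Elimination code 2080 applies this: "Non compliance with vaccination schedule for HRV and/or DPT-IPV vaccination".

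Section 2 describes the Co-administration arm in months: infants "will be administered the DPT-IPV vaccine according to a 3, 4, 6 month schedule". The Staggered arm has 3, 4.5 and 6 months. Table 4 requires only that Visit 2 take place at 3 months of age or later. An 8-week cap is stated once, for the Staggered arm's dose 1 to dose 2: "The period between Visit 2 and Visit 5 should be within 8 weeks". No reason is given for the 56-day limit between doses 2 and 3.

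Section 6.3.1 states: "The ATP cohort for immunogenicity will be used for the primary analysis of immunogenicity". A TVC analysis of immunogenicity follows only if more than 5% of vaccinated subjects with results are excluded from that cohort. The rule is not split by arm.

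**The concern.** An ATP window should allow for ordinary scatter around the day that sites are told to aim for. Here one arm is aimed at the edge of its window and the other at a point 11 days inside it. A one-day delay, for a cold or a clinic closure, removes the infant in the test arm and has no effect in the control arm. Exclusion from the primary cohort then depends on the assigned arm, for a reason unrelated to the co-administration question.

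That cohort carries all seven non-inferiority comparisons, which Section 7 interprets in a fixed order, so a failure early in the sequence blocks what follows. The stakes are precision lost on one side only and a comparison of two cohorts filtered with different strictness relative to their own schedules. The SAP gives no basis for saying which way any bias would run.

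**Working it through.** **1. Room after target (upper allowed limit minus optimal length, Table 4)**

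| Arm | Interval | Limit − target | Days |
|---|---|---|---|
| Co-administration | Visit 1→2 | 42 − 30 | 12 |
| | Visit 2→4 | 42 − 30 | 12 |
| | **Visit 4→6** | **56 − 56** | **0** |
| | Visit 6→7 | 48 − 30 | 18 |
| Staggered | Visit 1→2 | 42 − 30 | 12 |
| | Visit 2→3 | 21 − 15 | 6 |
| | Visit 3→5 | 42 − 30 | 12 |
| | **Visit 5→6** | **56 − 45** | **11** |
| | Visit 6→7 | 48 − 30 | 18 |

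Day 56 itself is allowed; exclusion starts on day 57.

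**2. Against the months in Section 2**

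For every birth date from 2015 to 2018, the count from the 4-month to the 6-month birthday is 59, 60, 61 or 62 days. Doses on those exact dates are 3 to 6 days past the limit. Elsewhere Table 4 converts 0.5, 1 and 1.5 months to 15, 30 and 45 days; on that rule 2 months would be 60, not 56. The Co-administration targets sum to 30 + 30 + 56 + 30 = 146 days and the Staggered targets to 30 + 15 + 30 + 45 + 30 = 150.

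The nominal schedule can still be met. From 3 to 6 months of age is 89 to 92 days. The targets for Visit 2→4 and Visit 4→6 sum to 30 + 56 = 86. If Visit 2 falls 3 to 6 days after the 3-month birthday and both targets are met, dose 3 is given at 6 months of age and the infant stays in the cohort. Visit 2→4 may also run to 42 days.

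**3. Possible size of the loss**

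Assumption, not in the SAP: intervals scatter normally around the day aimed for, rounded to whole days, with SD 2, 4 or 7 days. The late share is 1 − Φ((56.5 − aim)/SD).

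| Aim | SD 2 | SD 4 | SD 7 |
|---|---|---|---|
| Co-administration, day 56 | 40.1% | 45.0% | 47.2% |
| Co-administration, day 49 (booked a week early) | 0.0% | 3.0% | 14.2% |
| Staggered, day 45 | 0.0% | 0.2% | 5.0% |

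**4. Power per antigen**

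Assumptions: 131 evaluable infants per arm (146 less about 10% for other reasons), equal true rates in both arms, and a further loss in Co-administration only. The figure is the exact binomial probability that the score 95% lower limit (method six in Annex 1) is at least −10 points.

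| Further loss (n) | 0% (131) | 10% (118) | 20% (105) | 30% (92) | 40% (79) |
|---|---|---|---|---|---|
| True rate 98% | 99.6 | 99.2 | 97.7 | 96.5 | 93.1 |
| True rate 95% | 92.2 | 89.5 | 86.0 | 79.2 | 74.6 |
| True rate 90% | 73.4 | 70.6 | 66.1 | 61.2 | 55.8 |

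**5. The TVC trigger**

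If all 292 infants have results, 14 exclusions give 14/292 = 4.79% (no TVC analysis) and 15 give 15/292 = 5.14% (TVC analysis). Fourteen exclusions all in Co-administration are 14/146 = 9.6% of that arm. This example assumes no other exclusions, so it is separate from the power illustration. There, the 10% already lost would itself start the TVC analysis if most of those infants had results.

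**The case against.** The strongest case is that 56 days is deliberate. It is 8 weeks, the cap stated for the Staggered dose 1 to dose 2 interval; no DPT-IPV interval in Table 4 may exceed it; and the table refers readers to the package inserts. The limit is also the same number in both arms, so a 57-day interval is excluded in either. This may well explain the limit. It does not explain the target: if 56 days is a ceiling, sites should be aimed below it, as they are in the Staggered arm.

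A reader might infer that Table 4 contradicts Section 2 and that infants who follow the stated schedule are dropped. The SAP does not support that. The months are nominal, Visit 2 has only a lower age limit, and step 2 shows dose 3 at 6 months of age inside the window. Only doses at exact 4- and 6-month birthdays are excluded.

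A reader might also infer that nearly half the test arm will be lost. That rests wholly on assumed scatter around day 56, while the window leaves 28 days of earlier room, and sites that book a week early lose far fewer. A loss of 40 to 47% of that arm would be about 20 to 24% of all infants and would start the TVC analysis. A loss small enough to escape the trigger, about 10% of one arm, costs about 0.4 to 2.8 points of power per antigen.

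Finally, any imbalance would be visible, because Section 6.1.1 tabulates interval deviations by group. That is true, but tabulation does not alter who is in the primary cohort, and the ATP result stays primary even when the TVC analysis is run.

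**Conclusion.** The point holds as a defect in one row of Table 4. Room after target is 0 days in Co-administration and 11 in Staggered, so a one-day delay removes an infant from the primary cohort in the test arm only. This follows from the table and its footnotes without further assumption.

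The size is not known. Under the assumed scatter, late exclusions in Co-administration run from about none to 47%, depending mainly on whether sites aim at day 56 or earlier. The power cost depends further on assumed true rates: slight at 98% unless the loss is large, material at 90 or 95% if 20% or more of the arm is lost. No direction of bias can be stated.

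The TVC check limits the harm from a large loss but can miss a moderate one confined to one arm. The row should be corrected: the change is cheap, and the study is open-label, so a later change could look influenced by the exclusions seen.

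**What to change.** Make these changes before exclusions by arm are reviewed.

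1. **One wider ATP limit in both arms.** In Section 5.2.2, set the same adapted ATP window for Visit 4→6 and Visit 5→6, for example 28 to 67 days (56 + 11 = 67). Record it in Section 9, which already logs a change to the ATP definition, and report intervals above 56 days by arm with the deviations in Section 6.1.1. Widening Co-administration alone would not do: the cohort rule would then admit 57- to 67-day intervals in the test arm only. With a common limit, room after target becomes 11 days in Co-administration and 67 − 45 = 22 in Staggered. Under the assumed scatter, late exclusions in Co-administration fall to 0.0, 0.2 and 5.0%.
2. **If 56 days is a labelled ceiling that must also define the ATP cohort,** keep it and move the Co-administration target to, for example, 45 to 49 days, which leaves 7 to 11 days. The SAP does not give the labelled maximum for this interval, so check it first.
3. **TVC trigger by arm.** In Section 6.3.1, run the TVC analysis if more than 5% are excluded in either arm or overall.

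Cost: two table rows, one line in Section 9 and one clause in Section 6.3.1. Option 1 leaves the objective, margin, method, dosing schedule and data collection unchanged, but some third doses given after 56 days enter the ATP cohort. Option 2 changes the instruction to sites and brings the third dose 7 to 11 days earlier. The per-arm trigger makes a TVC analysis somewhat more likely.

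### Infants enrolled at 42 to 46 days of age (up to 49 days for some birth dates) have no Visit 2 date that meets both the 28-42 day interval and the 3-month age footnote in SAP Table 4

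*SAP*

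**What the plan says.** Three provisions of the SAP bear on the timing of Visit 2.

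- **Enrolment age** (section 2, Table 1), the same in both groups: "Co-administration group | 146 | 6 weeks - 12 weeks | x" and "Staggered group | 146 | 6 weeks - 12 weeks | x".
- **Visit interval** (section 5.2.2, Table 4), also the same in both groups: "Visit 1→Visit 2* | 30 days | 28 days - 42 days". The first figure is the optimum and the second is the allowed range. Footnote 2 makes subjects ineligible for the ATP immunogenicity cohort "if they make the study visit outside this interval". The matching elimination code, 2080, reads "Non compliance with vaccination schedule for HRV and/or DPT-IPV vaccination – see Table 4".
- **Age at Visit 2** (asterisk on that same Table 4 row): "Visit 2 should take place when the subject is 3 months of age or older".

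Section 6.3.1 makes the ATP cohort the primary immunogenicity set. It adds a TVC analysis only if more than 5% of vaccinated subjects with results are excluded from the ATP cohort. Section 6.1.1 tabulates age and interval deviations by group. Section 11.2.3 defines age only as a number of units since birth, so nothing in the SAP converts 3 months into days.

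**The concern.** The interval and the age footnote sit on one row of one table, and that table is the working definition of code 2080. For the youngest eligible infants they appear to be incompatible. If so, whether such an infant enters the primary non-inferiority analysis depends on which provision the site followed, and the SAP does not say which prevails.

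A site that waits until the infant is 3 months old goes past 42 days, and the infant is excluded. A site that stays within 42 days sees the infant too young. The age footnote has no elimination code of its own, and the SAP does not state whether code 2080, by pointing to Table 4, is meant to cover it. The trial is open-label, so this is better settled in advance than case by case.

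**Working it through.** The SAP gives no figure of its own to reproduce here. The check is date arithmetic.

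**Inputs**
- Youngest age at Visit 1: 6 weeks = 42 days (Table 1, taken as age at Visit 1).
- Oldest age at Visit 1: 12 weeks = 84 days, so 84 − 42 + 1 = 43 eligible days of age.
- Longest allowed Visit 1→Visit 2 interval: 42 days (Table 4, both groups).
- Age floor at Visit 2: 3 months. Over every birth date in 2016-2017, three calendar months came to 89 days (29 dates), 90 (124), 91 (156) or 92 (422), for 731 dates in all. A 12-week (84-day) reading is added as a sensitivity case.

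**Step 1. Oldest compliant age at Visit 2 for the youngest infant.** 42 + 42 = 84 days. This is 5 to 8 days short of 89-92.

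**Step 2. Lowest enrolment age that can meet both rules.** Lowest age = (3 months in days) − 42.

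| 3 months taken as | Lowest workable age at Visit 1 | Ages with no compliant date | Share of the 43 days |
|---|---|---|---|
| 84 days | 42 | none | 0 |
| 89 days | 47 | 42-46 (5 days) | 5/43 = 11.6% |
| 90 days | 48 | 42-47 (6 days) | 6/43 = 14.0% |
| 91 days | 49 | 42-48 (7 days) | 7/43 = 16.3% |
| 92 days | 50 | 42-49 (8 days) | 8/43 = 18.6% |

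On the 84-day reading a 42-day-old has exactly one compliant date, day 42 after Visit 1.

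**Step 3. Interval that a 42-day-old would need.** 89 − 42 = 47 to 92 − 42 = 50 days, against a limit of 42.

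**Step 4. The optimum interval.** Reaching 3 months at the 30-day optimum needs an age at Visit 1 of 89 − 30 = 59 to 92 − 30 = 62 days, which is about 2 months. The nominal schedule in section 2 (first HRV dose at 2 months, second at 3 months in the Co-administration group) is therefore consistent with Table 4. The conflict arises only at the low end of the eligible range.

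**Step 5. Sensitivity to the upper age.** If 12 weeks means 12 completed weeks (up to 90 days, so 49 eligible days), the shares become 5/49 = 10.2% to 8/49 = 16.3%.

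**The case against.** The best case against this point is that no infant is forced out of the ATP cohort. The footnote is worded as a recommendation, footnote 2 ties exclusion to the interval alone, and no elimination code names age at Visit 2. An infant seen on day 42 keeps the interval and, on a plain reading, stays in. **This stands.** Exclusion is one of two outcomes, and the other is an age departure with no stated consequence.

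Other parts of the objection also stand:

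- **Headcount.** A reader might infer a loss of 34 to 54 of the 292 infants (5/43 and 8/43 of 292). That needs enrolment spread evenly over 42-84 days and every affected infant excluded. The SAP supports neither, and the nominal 2-month first dose suggests fewer in the band.
- **Template 6.** Its median of 7 weeks at dose 1 might suggest that enrolment clusters at the low end. Section 13 says the templates were copied from other studies for illustration, so it says nothing about this trial.
- **Bias.** A reader might infer a bias in the comparison. The rule is identical in both randomised groups, and none is shown.
- **Irrelevance of the limit.** DPT-IPV starts at Visit 2, so the limit does not alter spacing between DPT-IPV doses. It might therefore seem irrelevant to the primary question. But in the Co-administration group it is the interval between the two HRV doses, and ATP membership requires compliance with the HRV schedule.
- **Existing safeguards.** Deviations are already tabulated by group, and a large ATP loss already triggers the TVC analysis.

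The safeguards do not remove the problem. The 5% trigger (0.05 × 292 = 14.6, so 15 infants if all had results) pools every reason for exclusion. The deviation table does not identify infants who had no compliant date.

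**Conclusion.** The conflict is real on the SAP's own figures, in both groups. If 3 months means calendar months and Table 1 gives age at Visit 1, infants enrolled at 42-46 days have no compliant Visit 2 date whatever their birth date. The band extends to 49 days where the three months span 92 days. On a 12-week reading the conflict shrinks to a single permitted day for a 42-day-old.

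The number of infants affected is unknown. The 12-19% figure is a share of the eligible age range, not a forecast, and if few infants enrol before about 7 weeks the loss is small. The likely consequence is some loss of ATP subjects, hence of precision, and inconsistent handling of similar infants. The documents do not support a claim that this age band will be removed from the primary analysis or that the group comparison will be biased. It still merits correction before analysis, because it bears on who enters the primary cohort and is cheap to settle.

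**What to change.** - Reconcile the three passages (enrolment age in Table 1, Visit 1→Visit 2 allowed interval in Table 4, age footnote in Table 4) so that every eligible enrolment age has at least one compliant Visit 2 date. Which rule prevails is for the sponsor, and this review does not choose between them.
- Define 3 months in days.
- State before analysis how code 2080 applies to infants whose only departure arises from this conflict, whether they exceeded the interval or were seen below the age in the footnote.
- Report the number of such infants by group.
- Add a sensitivity analysis of the primary endpoints that keeps them in.

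The cost is SAP wording and one small extra analysis, with no additional visits, data or subjects.
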